## 9. HANDLING OF MISSING DATA

All imputations specified in this section will be performed for the Double-Blind Treatment and titration Period only; the Post-treatment Follow-Up Period data will be analyzed as observed.

For the analyses of the co-primary endpoints (PASI-75 and IGA), multiple imputation (MI) will be the primary imputation method. The modified non-responder imputation (m-NRI) and last observation carried (LOCF) method will be used as sensitivity analyses.

Details of the imputation methods are as following:

- **MI:** Missing data will be imputed using multiple imputations, a simulation-based approach where missing values are replaced by multiple Bayesian draws from the conditional distribution of missing data given the observed data and covariates, creating multiple completed data sets. These completed datasets can then be analyzed using standard analysis methods. MI will be implemented for all subjects with missing data, included those who used rescue medications or discontinued due to unsatisfactory therapeutic effect.

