### 11.4 Analysis Visit Window

Efficacy and safety endpoints will be analyzed according to their windowed visits defined by actual study day. If more than one visit occurs within a single visit window, then the analysis will take the one closest to the target day. If the 2 visits are equidistant from the target day, the later visit will be used. A later visit within the window will be used for LOCF.

The following analysis visit windows will apply:

Visit	Week	Target Day	Efficacy Assessment Window	Safety Assessment Window
2	Baseline	0	On or prior to date of first dose	On or prior to date of first dose
3	4	28	Post-dose – Day 42	Post-dose – Day 42
4	8	56	Day 43 – Day 70	Day 43 – Day 70
5	12	84	Day 71 – Day 98	Day 71 – Day 98
6	16	112	Day 99 – Day 126	Day 99 – Day 126
7	20	140	Day 127 – Day 154	Day 127 – Day 154
8	24	168	≥Day 155	≥Day 155
9 (Follow-Up)	25	LD+7	> LD+15	> LD+15

LD = Last dose date

Visits 3 through 8 are on-treatment visits. Therefore, only on-drug assessments or assessments performed within 15 days post last dose are to be analyzed within those windows, according to their actual study day. Visit 9 is an off-treatment visit, which will be analyzed according to their number of days after last dose, regardless of the actual study day. For example, a subject who has Visit 4 on Day 56, then discontinues with last dose on Day 84 and returns for Early Termination on Day 100 will have no data within the Visit 6 window. The Early Termination visit must be analyzed as Visit 9. For this subject, data for Visits 5, 6, 7, and 8 would be carried forward from Visit 4 in an LOCF analysis. If the last dose date is unknown, then all visits will be analyzed as on-treatment based on actual study day (i.e., no Visit 9 will be identified for the subject).

Subjects who permanently discontinue the study drug for any reason or who withdraw from the study prematurely prior to the end of the Double-Blind Treatment Period should undergo the ETV followed by the EOS Safety Follow-up Period Visit. In the event that the ETV or Week 24 Visit occurs > 1 week following the last dose of the study drug, the EOS Safety Follow-up Visit may not be required. If necessary, the Investigator may decide to extend the EOS Safety Follow-up Visits beyond 1 week to monitor recovery of safety parameters (eg, lymphopenia).

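### SAP 11.4 sets the Visit 9 (Follow-Up) target at LD+7 but its window at > LD+15, so follow-up visits fall into treatment windows and can supply the Week 24 co-primary value

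*SAP*

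**What the plan says.** SAP 11.4 assigns efficacy and safety data to analysis visits by actual study day. Week 24 (Visit 8) has target Day 168 and takes everything from Day 155 onward. Visit 9 (Follow-Up) has target LD+7, and both its efficacy and safety windows are > LD+15.

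The text repeats the 15-day cut for Visits 3 to 8: "only on-drug assessments or assessments performed within 15 days post last dose are to be analyzed within those windows". It also states that "Visit 9 is an off-treatment visit". Where two visits share a window, the one nearer the target is taken. On ties, "If the 2 visits are equidistant from the target day, the later visit will be used", and separately "A later visit within the window will be used for LOCF". A further rule reads: "If the last dose date is unknown, then all visits will be analyzed as on-treatment based on actual study day". In that situation the subject has no Visit 9 at all.

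SAP section 9 treats follow-up as a separate period: "All imputations specified in this section will be performed for the Double-Blind Treatment and titration Period only", and "the Post-treatment Follow-Up Period data will be analyzed as observed".

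Protocol Table 1-1 and section 7.2.5 place the follow-up visit 1 week (+3 days) after Week 24 or the early termination visit (ETV), with PASI and IGA collected. The protocol synopsis and SAP section 3 give the tolerance as ±3 days.

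**The concern.** The target day lies outside its own window. A follow-up visit held on target is too early to be Visit 9, so by default it goes to one of Visits 3 to 8. The row in effect excludes the visit it is named for.

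This reaches the co-primary endpoints because PASI and IGA are taken at follow-up, assignment ignores the nominal visit label, and the Week 24 window has no upper day limit. A score from a visit described as off-treatment could then count as observed Week 24 data in the FAS analysis. It would either pre-empt a multiple imputation or displace the scheduled or ETV score. The sample size section assumes 50% dropout, so subjects with an ETV and a follow-up visit are not a fringe group.

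LOCF raises a second question. Section 11.4 prefers the later visit within a window, which may be the follow-up. Section 9 separates follow-up data from the imputation period. Two programmers could reasonably build different LOCF datasets.

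**Working it through.** **Inputs.** Windows, tie rule and 15-day cut: SAP 11.4. Follow-up timing: 7 to 10 days after Week 24/ETV (Protocol 7.2.5) or 4 to 10 days (SAP section 3). Gap from last dose to Week 24/ETV: taken as 0 to 7 days, because SAP 11.4 says follow-up may be waived "In the event that the ETV or Week 24 Visit occurs > 1 week following the last dose of the study drug". Notation: g = gap, d = study day of Week 24/ETV, f = days from there to follow-up. Follow-up is then at LD + g + f, on study day d + f. The counts below are unweighted day combinations, not subjects.

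**The SAP's own example.** Last dose Day 84, ETV Day 100: 100 − 84 = 16 > 15, so Visit 9, as the SAP says. One day earlier, Day 99 (LD+15), would be Visit 6. The > LD+15 cut is therefore the operating rule and not a stray table entry.

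**Does follow-up reach Visit 9?** Only if g + f > 15.
- f = 7: g + f runs from 7 to 14, so 8 of 8 are within LD+15.
- f = 7 to 10: 8 + 8 + 7 + 6 = 29 of 32 within LD+15. The exceptions (g, f) are (6, 10), (7, 9) and (7, 10).
- f = 4 to 10: 24 + 29 = 53 of 56 within LD+15.
- With last dose on Day 168, scheduled follow-up on Day 175 to 178 is always in the Visit 8 window. Visit 9 starts at Day 184.

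**Case (a): ETV in the Visit 7 window, follow-up in the Visit 8 window.** This requires d ≤ 154, d + f ≥ 155 and g + f ≤ 15.

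| f | ETV days | Pairs | Gaps allowed | Combinations |
|---|---|---|---|---|
| 7 | 148–154 | 7 | 0–7 | 56 |
| 8 | 147–154 | 8 | 0–7 | 64 |
| 9 | 146–154 | 9 | 0–6 | 63 |
| 10 | 145–154 | 10 | 0–5 | 60 |

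The total is 34 pairs and 243 of 34 × 8 = 272 combinations (89%). Example: last dose Day 150, ETV Day 152 (Visit 7), follow-up Day 159 (LD+9, Visit 8).

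**Case (b): Week 24/ETV on Day 155 to 164, follow-up as close or closer to Day 168.** This requires |d + f − 168| ≤ |d − 168|.
- f = 7 to 10: 38 of 40 pairs qualify; d = 164 fails with f = 9 or 10. Adding g + f ≤ 15: Days 155–163 give 9 × 29 = 261 and Day 164 gives 2 × 8 = 16, so 277 of 320 (87%). Example: Day 161 is 7 days from target and follow-up on Day 168 is exactly on it.
- f = 4 to 10: 9 × 53 + 5 × 8 = 517 of 560 (92%).

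**Case (c): Week 24 missed, follow-up attended within LD+15.** If it falls on Day 155 or later, follow-up is the only candidate for Visit 8.

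**Completers assessed on Day 165 to 171.**
- f = 7 to 10: 0 of 28 pairs displaced.
- f = 4 to 10: 4 of 49 pairs displaced, with (Week 24 day, follow-up day) = (165, 169), (165, 170), (165, 171) and (166, 170). All gaps stay within LD+15, so 4 × 8 = 32 of 392 combinations (8%).

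**LOCF.** Last dose Day 100, ETV Day 103, follow-up Day 110: both visits are in the Visit 6 window. Section 11.4 carries the Day 110 value forward to Week 24.

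**The case against.** The strongest reply is that the 15-day cut is deliberate. Table, text and example agree on it, so an assessment at LD+9 is on-treatment by definition and the only slip is the LD+7 cell. That would explain the cut. It does not explain a row labelled Follow-Up with an LD+7 target, nor section 9's separate handling of follow-up data. A 15-day allowance for late scheduled or ETV assessments does not require admitting the follow-up visit.

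Several narrower points do stand:
- **LOCF.** Section 9 says which periods are imputed, not which observations may be carried forward. This is a tension that allows two readings rather than a flat contradiction, and LOCF is a sensitivity analysis.
- **Frequency.** The routes to Week 24 are narrow, and the percentages are conditional on already being in one of the cases. They are not risks.
- **Gap range.** Protocol 4.1 waives follow-up when the ETV is 1 week or more after last dose, while SAP 11.4 says more than 1 week. Dropping g = 7 gives 27 of 28 within LD+15, and case (a) becomes 49 + 56 + 63 + 60 = 228 of 34 × 7 = 238. The conclusion does not change.
- **Other analyses.** m-NRI overrides the value for rescue users and for dropouts due to lack of efficacy. The PP rule on the Week 24 allowable window would help if that window means Day 168 ±3 as in Protocol Table 1-1, but the SAP does not say so. Neither protects the primary FAS analysis with MI.
- **Classification by label.** Under the fix, an ETV at LD+14 counts as on-treatment while a follow-up at LD+7 does not. That is a real asymmetry, accepted in order to keep follow-up data separate as section 9 describes.

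**Conclusion.** The concern holds. Followed as written, SAP 11.4 sends almost every scheduled follow-up visit to a treatment window: 29 of 32 timing combinations on the +3-day schedule and 53 of 56 on the ±3-day schedule, for gaps of 0 to 7 days. In cases (a) to (c) that visit supplies the observed Week 24 PASI and IGA.

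The exposure lies with late discontinuers, early or missed Week 24 visits, and subjects with an unknown last dose date. Completers seen on Day 165 to 171 keep their Week 24 score on the +3-day schedule, so the two statements of the follow-up tolerance also need to be reconciled.

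The documents give neither the distribution of visit timing nor the rate of change in PASI or IGA off drug. The number of subjects affected and the size and direction of any bias therefore cannot be derived. The rule should be corrected before unblinding, because it determines how the co-primary dataset is built.

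**What to change.** Before unblinding, amend SAP 11.4 as follows:

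- Define Visit 9 as the nominal end-of-study safety follow-up visit on any day after last dose, plus any other assessment later than LD+15. The row then contains its own target, and the worked example (ETV at LD+16) still goes to Visit 9.
- Exclude the nominal follow-up visit from the Visit 3 to 8 windows and as a source for LOCF, including when the last dose date is unknown.
- Keep the 15-day allowance for scheduled and early termination visits.
- State that this follows section 9. It also fits Protocol 8.7.3, which maps early termination data to a treatment visit but has no such rule for follow-up.
- Since the row has both an efficacy and a safety column, say whether the change applies to both.

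The cost is one table row, a few sentences and the matching programming. The downside is that a few more Week 24 values will be missing and therefore imputed.

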## 11.5 Pooled Analysis Centers

There will be approximately 75 trial sites in the United States. Pooling of trial sites, based on insufficient number of subjects, will be performed when any site does not have a minimum number (e.g., 5 subjects per site per arm) of subjects in the FAS population. Sites with insufficient number

of subjects will be combined in order of geographical proximity. The exact composition of these “analysis sites” will be determined and documented prior to breaking the trial blind.

Descriptive summaries of the co-primary efficacy endpoints will be provided for each analysis site. Any notable site heterogeneity will be further investigated. Exploratory analyses of the co-primary endpoints may be performed excluding analysis sites whose results differ appreciably from other analysis sites.

## **12. STATISTICAL EVALUATION**

### **12.1 Subject Disposition**

The number and percentage of subjects screened, randomized, included in each analysis population, completing the study, withdrawing from the study (together with the reasons for withdrawal), and subjects excluded from PP population (together with the reasons for exclusion) will be summarized using frequencies and percentages by treatment group. A by-subject listing will be presented for all subject enrollment and disposition. Screen failures and subjects not randomized will also be presented in by-subject listings.

The number of days in the study (date of study completion / discontinuation minus date of Day 1 plus 1) will be summarized using descriptive statistics for each treatment group.

### **12.2 Protocol Deviation**

Protocol deviations will be provided in a by-subject listing.

### **12.3 Demographic and Baseline Characteristics**

Demographics and baseline characteristics will be summarized overall and by treatment for the FAS, PP and Safety populations. The following demographic and baseline variables will be included:

- Age
- Gender
- Race
- Ethnicity
- Weight
- Height
- Waist circumference
- BMI
- Baseline PASI score
- Baseline BSA
- Baseline IGA

## 12.4 Study Medication Exposure and Compliance

The following exposure and compliance parameters will be summarized by treatment group and study period (overall, titration, and treatment as applicable) using descriptive statistics:

- Total number of days exposed to study medication, defined as date of last dose of study drug during the study minus date of first dose of study drug plus 1.
- Total number of tablets taken during the titration period (Week 1 – 5), defined as number of dispensed tablets from blister wallets minus number of returned tablets from blister wallets.
- Total number of tablets taken during the treatment period (Week 6 – 24), defined as total number of dispensed tablets from bottles minus total number of returned tablets from bottles.
- Number of tablets per bottle taken during the treatment period (Week 6 – 24), defined as number of dispensed tablets per bottle (total of 4 bottles per visit) minus number of returned tablets per bottle.
- Total number of tablets taken, defined as the summation of number of tablets taken during the titration and treatment period.
- Percent compliance will be calculated as the number of tablets taken divided by the expected number of tablets, defined for the titration period, treatment period, and overall. The expected number of tablets are as following:

Period	Number of Tablets Dispensed Per Dosing Regimen	Expected Total Number of Tablets
Titration (Week 1 – 5)	Week 1 – 4: 28 per week Week 5: 35 per week	$28*4 + 35 = 147$
Treatment (Week 6 – 24)	42 per week	$42*19 = 798$
Overall (Week 1 – 24)		945

- Subject compliance, defined as 80% - 120% (inclusive) in percent compliance. If the percentage of study medication compliance is unknown, the subject is assumed to be non-compliant with study medication. Subject compliance is summarized by periods and overall. Overall compliance will be the main determinant of compliance.
- Average daily dose of IP received can be calculated as the number of tablets divided by the number of days exposed to study medication. The average daily dose of IP received by each subject will be summarized by treatment group using summary statistics for the overall period.

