Week 3 (Days 15-21)	100 P (am) + 100 P (am) 200 (pm) + 200 (pm)	100 P (am) + 100 (am) 200 P (pm) + 200 (pm)	100 (am) + 100 (am) 200 (pm) + 200 (pm)	100 P (am) + 100 P (am) 200 P (pm) + 200 P (pm)
Week 4 (Days 22-28)	200 P (am) + 200 P (am) 200 (pm) + 200 (pm)	200 P (am) + 200 (am) 200 P (pm) + 200 (pm)	200 (am) + 200 (am) 200 (pm) + 200 (pm)	200 P (am) + 200 P (am) 200 P (pm) + 200 P (pm)
Week 5 (Days 29-35)	200 P (am) + 200 P (am) 200 (pm) + 200 (pm) + 200 P (pm)	200 P (am) + 200 (am) 200 (pm) + 200 (pm) + 200 P (pm)	200 (am) + 200 (am) 200 (pm) + 200 (pm) + 200 (pm)	200 P (am) + 200 P (am) 200 P (pm) + 200 P (pm) + 200 P (pm)

Table 6-2 Titration Regimen

Visit	Weeks (Days)	Tablet regimen for all groups
Baseline*	Week 1 (Days 1-7)	Take 2 tabs in the morning and 2 tabs in the evening from the blister
	Week 2 (Days 8-14)	Take 2 tabs in the morning and 2 tabs in the evening from the blister
	Week 3 (Days 15-21)	Take 2 tabs in the morning and 2 tabs in the evening from the blister
	Week 4 (Days 22-28)	Take 2 tabs in the morning and 2 tabs in the evening from the blister
	Week 5 (Days 29-35)	Take 2 tabs in the morning and 3 tabs in the evening from the blister
Week 4# (Day 28)	Week 6 (Days 36-42) to Week 8 (Days 50-56)	Take 1 tab from AM Bottle 1 and 2 tabs from AM Bottle 2; repeat the process in the night with PM bottles.

* = Subjects will be given 5 blister wallets (for Weeks 1-5)

= Subjects will be given 2 sets of 2 Bottles as mentioned.

Table 6-3 Treatment Schedule: Treatment Period (Weeks 6-24)

Visit	PPC-06 400 mg QD Regimen	PPC-06 400 mg BID Regimen	PPC-06 600 BID Regimen	PPC-06 Placebo BID Regimen
	Week 6 – Week 24	Week 6 – Week 24	Week 6 – Week 24	Week 6 – Week 24
Weeks 8-20 (Dispense 2 sets of 2 Bottles) ¹	200 P (am) + 200 P (am) + 200 P (am) 200 (pm) + 200 (pm) + 200 P (pm)	200 P (am) + 200 (am) + 200 (am) 200 (pm) + 200 (pm) + 200 P (pm)	200 (am) + 200 (am) + 200 (am) 200 (pm) + 200 (pm) + 200 (pm)	200 P (am) + 200 P (am) + 200 P (am) 200 P (pm) + 200 P (pm) + 200 P (pm)

¹ Subjects will be given 2 sets of 2 bottles (2 morning (AM) bottles + 2 evening (PM) bottles)

AM Bottles: AM Bottle 1 (30 count) and AM Bottle 2 (60 count)

PM Bottles: PM Bottle 1 (30 count) and PM Bottle 2 (60 count)

Take 1 tablet from (AM) Bottle 1 and 2 tablets from (AM) Bottle 2; repeat the process in the evening with (PM) bottles

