6.4 Packaging and Labeling

The IP will be labeled according to all applicable federal regulations and be printed in the local language.

The study medication will be supplied to the clinical site(s) in kits containing 5 weeks of blister wallets which will be used for the Titration Period, as well as kits containing 2 sets of 2 Bottles which will be used for the Treatment Period. The blister wallet kits will contain a total of 147 tablets, and the Bottle kits will contain 2 AM and 2 PM bottles:

- AM Bottle 1 – 30 tablets
- AM Bottle 2 – 60 tablets
- PM Bottle 1 – 30 tablets
- PM Bottle 2 – 60 tablets

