## 8. ANALYSIS POPULATIONS

The following analysis sets/populations will be used in this trial:

- Safety population: include all subjects who receive at least one dose of IP. The safety population is the population used for all safety analyses.
- Full analysis set (FAS) – All randomized subjects who receive at least one dose of investigational product and have at least one post dose efficacy assessment. The FAS population will be the primary population for the efficacy analyses
- Per Protocol (PP) population: include subjects in the FAS population who complete the study without any major protocol violations that are considered likely to affect the efficacy analysis outcomes of the study. Major protocol violations will include but not be restricted to the following:
  - Failure to meet the inclusion/exclusion criteria that are considered likely to affect the efficacy analysis outcomes of the study
  - Randomization error

- Usage of any prohibited concomitant medications or procedures
- Failure to have Week 24 assessment within the allowable window for either of the co-primary endpoints
- Failure to be compliant with treatment regimen

Additional criteria may be added to determine PP population. The composition of the PP population will be determined and documented in blind reviews of the database conducted prior to unblinding the study database. Subjects who used rescue medications or who discontinued due to unsatisfactory therapeutic effect will be included in the PP population. These subjects will be considered as treatment failures (i.e., non-responder for both PASI-75 and IGA) for all time points after the initiation of rescue medications or subject discontinuation.

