### 11.2 Study Day

Day 1 is defined as the date of first study drug administration. For subjects who used any study drug but did not have a recorded date of first study drug administration (e.g., due to missing Week 4 visit), Day 1 is defined as randomization date + 1. Study day is calculated relative to the date of Day 1.

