Yes	XX (XX.X)	XX (XX.X)	XX (XX.X)	XX (XX.X)
No	XX (XX.X)	XX (XX.X)	XX (XX.X)	XX (XX.X)

[1] Date of last dose of study drug during the study minus date of first dose of study drug plus 1

[2] Summation of number of tablets taken during the titration and treatment period

[3] Number of tablets taken divided by the number of days exposed to study medication.

[4] Number of tablets taken / number of expected tablets \*100. The expected total number of tablets is 945 for the whole study.

Table 14.1.3.2: Summary of Exposure and Compliance  
Titration Period (Week 1—5)  
Safety Population

	PPC-06 400 mg QD (N=XX)	PPC-06 400 mg BID (N=XX)	PPC-06 600 mg BID (N=XX)	Placebo (N=XX)
Total Number of Tablets Taken [1]				
N	XX	XX	XX	XX
Mean (SD)	XX.X (XX.X)	XX.X (XX.X)	XX.X (XX.X)	XX.X (XX.X)
Median	XX.X	XX.X	XX.X	XX.X
Minimum, Maximum	XX, XX	XX, XX	XX, XX	XX, XX
Percent Compliance (%) [2]				
N	XX	XX	XX	XX
Mean (SD)	XX.X (XX.X)	XX.X (XX.X)	XX.X (XX.X)	XX.X (XX.X)
Median	XX.X	XX.X	XX.X	XX.X
Minimum, Maximum	XX, XX	XX, XX	XX, XX	XX, XX
80-120% Compliant (Inclusive), n (%)				
N	XX	XX	XX	XX
Yes	XX (XX.X)	XX (XX.X)	XX (XX.X)	XX (XX.X)
No	XX (XX.X)	XX (XX.X)	XX (XX.X)	XX (XX.X)

[1] Number of dispensed tablets from blister wallets minus number of returned tablets from blister wallets.

[3] Number of used tablets / number of expected tablets for the titration period \*100. The expected total number of tablets is 147 for the titration period.

Generated on XX/XX/XX:XXXX by XXXXXX / Uses: XXXX / Reference: Listing XXXX

Table 14.1.3.3: Summary of Exposure and Compliance  
Treatment Period (Week 6 – 24)  
Safety Population

	PPC-06 400 mg QD (N=XX)	PPC-06 400 mg BID (N=XX)	PPC-06 600 mg BID (N=XX)	Placebo (N=XX)
Total Number of Tablets Taken [1]				
N	XX	XX	XX	XX
Mean (SD)	XX.X (XX.X)	XX.X (XX.X)	XX.X (XX.X)	XX.X (XX.X)
Median	XX.X	XX.X	XX.X	XX.X
Minimum, Maximum	XX, XX	XX, XX	XX, XX	XX, XX
Percent Compliance (%) [2]				
N	XX	XX	XX	XX
Mean (SD)	XX.X (XX.X)	XX.X (XX.X)	XX.X (XX.X)	XX.X (XX.X)
Median	XX.X	XX.X	XX.X	XX.X
Minimum, Maximum	XX, XX	XX, XX	XX, XX	XX, XX
80-120% Compliant (Inclusive), n (%)				
N	XX	XX	XX	XX
Yes	XX (XX.X)	XX (XX.X)	XX (XX.X)	XX (XX.X)
No	XX (XX.X)	XX (XX.X)	XX (XX.X)	XX (XX.X)

[1] Number of dispensed tablets from bottles minus number of returned tablets from bottles.

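### Percent compliance divides by a fixed 945 tablets whatever the time on drug, so it measures treatment duration rather than adherence

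*SAP*

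**What the plan says.** SAP 12.4 states: "Percent compliance will be calculated as the number of tablets taken divided by the expected number of tablets". This is done for titration, treatment and overall, and the accompanying table gives the expected counts as 147, 798 and 945. The compliant range is set by "Subject compliance, defined as 80% - 120% (inclusive) in percent compliance", an unknown percentage counts as non-compliant, and "Overall compliance will be the main determinant of compliance".

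The output shells repeat the constants. The footnote to Table 14.1.3.1 reads "The expected total number of tablets is 945 for the whole study", Tables 14.1.3.2 and 14.1.3.3 carry 147 and 798, and Listing 16.2.5.3 prints all three for each subject. Nothing in the SAP prorates for early discontinuation.

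SAP 8 lists "Failure to be compliant with treatment regimen" among the major violations that exclude a subject from PP. The same section keeps in PP those who took rescue medication or stopped for lack of effect.

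Protocol 6.8 works differently: at each visit, site staff compare tablets used with those expected in the interval since the previous visit. Protocol 8.5 refers to an expected number by period but gives no counts.

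**The concern.** An adherence measure should ask what share of the prescribed tablets a subject took while on treatment. With a fixed denominator, someone who took every tablet and stopped at Week 12 cannot be told apart from someone who stayed 24 weeks and took fewer than half.

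This matters because SAP 7 plans for 50% dropout. The compliance tables are run on the Safety Population, so every early stopper is in them. If discontinuation differs by arm, as it may for a drug with known gastrointestinal effects, the tables would show a difference in adherence that is really a difference in discontinuation. The same flag also feeds a PP exclusion.

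**Working it through.** **Inputs.** From SAP 12.4 and the Protocol 6.2 tables: 4 tablets a day on Days 1-28, 5 a day on Days 29-35 and 6 a day from Day 36. The last rate follows from "Take 1 tablet from (AM) Bottle 1 and 2 tablets from (AM) Bottle 2; repeat the process in the evening with (PM) bottles", that is 3 in the morning and 3 in the evening. SAP 11.2 fixes the clock: "Day 1 is defined as the date of first study drug administration".

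**The plan's own figure.** 28 × 4 + 7 × 5 = 147. Days 36-168 are 133 days, and 133 × 6 = 798. The sum is 945, so the total reproduces exactly.

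**Score of a fully adherent subject, by day of last dose.** Tablets = 147 + 6 × (day − 35), divided by 945.

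| Last dose | Tablets | Overall compliance |
|---|---|---|
| Day 56 (Week 8) | 273 | 28.9% |
| Day 84 (Week 12) | 441 | 46.7% |
| Day 112 (Week 16) | 609 | 64.4% |
| Day 136 | 753 | 79.7% |
| Day 137 | 759 | 80.3% |
| Day 168 (Week 24) | 945 | 100% |

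The lower limit is 0.80 × 945 = 756 tablets, first reached on Day 137.

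**By period.** For titration, 80% of 147 is 117.6: Day 29 gives 117 and Day 30 gives 122, so Day 30 is the first to pass. For treatment, 80% of 798 is 638.4: Day 141 gives 106 × 6 = 636 and Day 142 gives 107 × 6 = 642, so Day 142 is the first to pass.

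**Share of an arm affected.** The documents give 50% dropout but not its timing, so the timing is assumed.
- Uniform over 168 days: 0.50 × 136/168 = 40.5%.
- Constant hazard: 1 − exp(−ln 2 × 136/168) = 43%.
- If nearly all dropout is early, the share approaches 50%; if it is mostly after Day 137, it is far smaller.

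**Overlap with the other PP exclusions.** SAP 8 already requires study completion and a Week 24 assessment in window. Under SAP 11.4 the Week 24 window opens on Day 155, and an assessment more than 15 days after the last dose is not analysed there. A last dose on Day 136 allows assessments only to Day 136 + 15 = 151, so with a known last dose date such a subject has no Week 24 value in any case.

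**Upper limit.** 120% of 945 is 1134 tablets. Bottle kits hold 30 + 60 + 30 + 60 = 180 (Protocol 6.4), and five are dispensed at Visits 3-7 (Protocol 6.6.1, SAP 6). Supply is 147 + 5 × 180 = 1047, or 110.8% of 945. Prorated to a scheduled visit day, the largest possible ratios are 327/273 = 119.8% at Day 56, 507/441 = 115.0% at Day 84, 687/609 = 112.8% at Day 112, 867/777 = 111.6% at Day 140 and 1047/945 = 110.8% at Day 168.

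**The case against.** The best defence is that the share of planned tablets received is a legitimate exposure measure, and that Table 14.1.3.1 reports days exposed and average daily dose beside it, so a reader can separate short treatment from poor adherence. This is only partly right. Because of titration, the average daily count also moves with duration: a fully adherent subject averages 273/56 = 4.9 tablets to Day 56 and 945/168 = 5.6 to Day 168. The shells of Tables 14.1.3.2 and 14.1.3.3 have no exposure row, and the compliant Yes/No row is not adjusted at all.

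The other points made against the concern limit its reach and should be accepted.
- A reader might infer that the rule is what removes early terminators from PP. It is not: the completion and Week 24 criteria already do so.
- A reader might infer that correcting the denominator removes the conflict over lack-of-effect discontinuers. It does not, because they fail those other two criteria as well. The inclusion sentence in SAP 8 may also be read as overriding the list, although the SAP does not say so.
- A reader might infer that prorating restores the 120% limit. The ceiling comes from supply: a completer still cannot exceed 110.8% with five kits, and overall values above 120% become possible only for some stops between visits. Table 1-1 appears to carry a further dispensing mark at Week 24. A sixth kit would give 1227/945 = 129.8%, but this conflicts with dispensing at Visits 3-7.
- A reader might take Day 137 as absolute. Tablets taken are those dispensed minus those returned, and the SAP has no rule for unreturned bottles. If they count as taken, a subject who stops between Weeks 16 and 20 and returns nothing scores up to (147 + 4 × 180)/945 = 867/945 = 91.7%.

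**Conclusion.** The concern stands in limited form. The count of 945 is correct; using it for every subject is the fault. Percent compliance and the 80% flag follow duration of treatment, and a fully adherent subject with a last dose before Day 137 is labelled non-compliant, assuming prescribed dosing and return of unused tablets. About 40% to 43% of each arm would be affected at 50% dropout spread uniformly or with constant hazard, and the figure moves with the timing of dropout.

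The main damage is to the descriptive Safety Population tables. In PP, the rule adds a third exclusion that conflicts with the stated inclusion of lack-of-effect discontinuers, and of rescue users who stop early. The documents do not support reading this as a threat to the primary result, which is multiple imputation on the full analysis set; PP with modified non-responder imputation is supportive only. The change should be made, but it is not critical.

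**What to change.** In SAP 12.4, the footnotes to Tables 14.1.3.1-3 and Listing 16.2.5.3:

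1. Define expected tablets as the scheduled count from first dose to the subject's last dose date, by period and overall: 4 a day on Days 1-28, 5 a day on Days 29-35 and 6 a day from Day 36. A fully adherent subject then scores 100% at any stopping day, for example 441/441 at Day 84.
2. Use the SAP 11.2 rule when the first dose date is missing. Treat compliance as unknown when the last dose date is unknown; the existing SAP 12.4 default then counts that subject as non-compliant.
3. Leave subjects whose last dose is before Day 36 out of the treatment-period table, since they have no expected tablets in that period.
4. State how unreturned tablets are counted, and note that temporary reductions or interruptions under Protocol 6.3 still read as missed tablets.
5. If percent of the planned 945 is wanted, keep it as a separate, labelled exposure measure.

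In SAP 8, state that the completion, Week 24 and compliance exclusions do not remove the subjects whom that section says will be included.

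The cost is SAP wording, one derived variable and revised footnotes. First and last dose dates already feed the exposure variable, so no new data are needed. The downside is small: a very short exposure can score 100%, so compliance should be shown beside days exposed. The change should not be presented as making the 120% limit effective.
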